5.1.1.1.2 Pneumonitis

Pneumonitis has been observed in patients treated with tselisib. Symptoms associated with pneumonitis were reversible upon treatment with corticosteroids. Dose delay and modification guidelines for patients who experience pneumonitis are presented in [Table 5](#).

Table 5 Management Guidelines for Pneumonitis

Pneumonitis Grade	Intervention	Investigations	Taselisib/Placebo Dose Modification and Management
1	No specific therapy required	Consider infectious work-up ^a . CT scan and consider PFTs ^b . Repeat CT Q8W until return to baseline.	No change
2	Symptomatic only. Prescribe corticosteroids if cough is troublesome and infectious etiology is ruled out.	Infectious work-up ^a . CT scan. Repeat CT Q4W until return to baseline. Consider PFTs ^b and bronchoscopy.	Hold taselisib/placebo as long as corticosteroids are being given. If pneumonitis improves to Grade ≤ 1 and upon completion of any corticosteroid treatment, resume taselisib/placebo dosing at the same taselisib dose or one dose level lower per investigator evaluation. For recurrent Grade 2 event, resume taselisib/placebo dosing at one dose level lower.
3	Prescribe corticosteroids if infectious etiology is ruled out. Taper as clinically indicated.	Infectious work-up ^a . CT scan. Repeat CT Q4W until return to baseline. Consider PFTs ^b and bronchoscopy.	Hold taselisib/placebo as long as corticosteroids are being given. If pneumonitis improves to Grade ≤ 1 and upon completion of any corticosteroids, resume taselisib/placebo dosing at one dose level lower.
4	Prescribe corticosteroids if infectious etiology is ruled out. Taper as clinically indicated.	Infectious work-up ^a . CT scan. Repeat CT Q4W until return to baseline. Consider PFTs ^b . Bronchoscopy is recommended.	Permanently discontinue taselisib/placebo.

CT = computed tomography; PFT = pulmonary function test; Q4W = every 4 weeks; Q8W = every 8 weeks.

^a Such as for bacterial, viral, or fungal pneumonia (e.g. *Pneumocystis jirovecii* pneumonia or pneumonia aspergillus).

^b PFTs may be useful to monitor the effect of interventions such as dose reduction/discontinuation and corticosteroids, in conjunction with imaging (White et al. 2010). It is strongly recommended to perform disease monitoring according to guidelines from White et al. if possible or according to clinical practice.

5.1.1.1.3 Rash

Treatment-related rash is commonly manifested as maculo-papular with or without pruritus. The rash has usually resolved upon holding taselesib and/or giving supportive therapy (e.g., topical or systemic steroids). Dose delay and modification guidelines for patients who experience rash are presented in [Table 6](#).

Table 6 Management Guidelines for Rash

Grade of Rash	Taselesib/Placebo Dose Modification and Management Guidelines
1	Continue dosing at current taselesib/placebo dose, and monitor for change in severity. Consider prescribing topical corticosteroids ^a .
2	Hold taselesib/placebo. Treat rash with topical corticosteroids. Consider treatment of rash with oral corticosteroids ^b . Hold taselesib/placebo treatment as long as oral corticosteroids are being administered. If rash improves to Grade ≤ 1 and upon completion of any systemic corticosteroids, resume taselesib/placebo at the same dose or one dose level lower per investigator evaluation. For recurrent Grade 2 rash, resume taselesib/placebo at one dose level lower.
3	Hold taselesib/placebo Treat rash with topical corticosteroids and/or systemic corticosteroids (oral or intravenous). Hold taselesib/placebo as long as systemic corticosteroids are being administered. Consider dermatological consultation and skin biopsy. If rash improves to Grade ≤ 1 and upon completion of any systemic corticosteroids, resume taselesib/placebo at one dose level lower.
4	Permanently discontinue taselesib/placebo. Treat with topical corticosteroids and/or systemic corticosteroids. Consider dermatological consultation and skin biopsy.

^a Suggested topical steroids include hydrocortisone 2.5% to face twice daily, triamcinolone 0.1% or fluocinonide 0.1% cream to body twice daily.

^b Suggested oral steroids include methylprednisolone dose pack or prednisone 60 mg daily followed by a taper (e.g., 60 mg \times 2 days, 40 mg \times 2 days, 20 mg \times 2 days, etc.).

5.1.1.1.4 Hyperglycemia

Hyperglycemia has been observed in patients who received taselesib while participating in other studies. Hyperglycemia has been reversible upon holding taselesib and/or initiating anti-hyperglycemic medication (e.g., metformin).

Patients with diabetes requiring anti-hyperglycemic medication or who have a fasting blood glucose level > 125 mg/dL will be excluded from the study. HbA_{1c} and fasting glucose levels will be monitored at baseline, and regular monitoring of fasting glucose

levels will occur during the study. Dose delay and modification guidelines for patients who experience hyperglycemia are presented in [Table 7](#).

Table 7 Management Guidelines for Hyperglycemia

Grade of Hyperglycemia	Taselisib/Placebo Dose Modification and Management Guidelines
1 or 2	Initiation of or an increase ^a in the dose of an anti-hyperglycemic agent (e.g., metformin) and additional glucose monitoring will be implemented. Taselisib/placebo dosing may either be held or continued per investigator evaluation.
3 (asymptomatic)	Hold taselisib/placebo. Treat hyperglycemia per standard of care, including implementation of additional glucose monitoring and initiation of or an increase in the dose of an anti-hyperglycemic therapy (e.g., metformin). If improves to Grade ≤ 1 , may resume taselisib/placebo dosing at one dose level lower.
3 (symptomatic), 3 (requiring hospitalization), or 4	Hold taselisib/placebo. Treat hyperglycemia per standard of care, including implementation of additional glucose monitoring and initiation of or an increase in the dose of anti-hyperglycemic therapy. If improves to Grade ≤ 1 , may resume taselisib/placebo dosing at one dose level lower. For recurrent symptomatic Grade 3 or Grade 4 hyperglycemic event, taselisib/placebo must be permanently discontinued.

^a If initiated after randomization, because patients with diabetes who require anti-hyperglycemic medications are not eligible.

5.1.1.1.5 Potential Abnormal Liver Function Tests

Some patients have experienced elevations of liver function test results (e.g., AST or ALT) while receiving taselisib in prior clinical studies. Patients will be monitored throughout the study treatment for changes in liver function tests. Given the potential for hepatic toxicity, all patients must have adequate liver function as manifested by measurements of serum bilirubin and hepatic transaminases for initial and continued dosing. Separate criteria for eligibility are given for patients with hepatic metastases.

For new abnormal liver function test results (e.g., elevated AST or ALT), a standard clinical work-up to understand the etiology of the abnormality should take place per local guidelines. In many cases, elevated liver function test results may be a result of liver metastases, concomitant medications, or biliary obstruction. Dose delay and modification for patients who experience abnormal liver function test results can also follow the guidelines in [Table 8](#) if deemed clinically appropriate by the investigator.

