4.6.2 Study Drug(s) Discontinuation

Patients must discontinue study drugs if they experience any of the following:

- Any medical condition that the investigator or Sponsor determines may jeopardize the patient's safety if the patient continues to receive study drug(s)
- *Disease progression (as assessed by the investigator)*
- Unacceptable toxicity
- Non-compliance with protocol specified drug administration and follow-up tests

The primary reason for study treatment discontinuation should be documented on the appropriate eCRF. Patients who discontinue study treatment will not be replaced.

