5.1.1.1.9 Management of Other Clinically Significant Adverse Events

See [Table 8](#) for the dose modifications for other clinically significant adverse events.

Table 8 Taselisib/Placebo Dose Delay and Modification Guidelines for Other Clinically Significant Adverse Events

Grade	Taselisib/Placebo
3, first event	Hold taselisib/placebo until Grade \leq 1. Resume taselisib/placebo at the same dose or one dose level lower per investigator evaluation.
3, recurrent or 4, non-life threatening	Hold taselisib/placebo until Grade \leq 1. Resume taselisib/placebo dosing at one dose level lower.
4, life-threatening	Permanently discontinue taselisib/placebo. Single-agent fulvestrant may be continued per investigator evaluation.

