5.2.3 Adverse Events of Special Interest (Immediately Reportable to the Sponsor)

Adverse events of special interest are required to be reported by the investigator to the Sponsor immediately (i.e., no more than 24 hours after learning of the event; see Section 5.4.2 for reporting instructions). Adverse events of special interest for this study include the following serious and non-serious events:

- Cases of potential drug-induced liver injury that include an elevated ALT or AST in combination with either an elevated bilirubin or clinical jaundice, as defined by Hy's law (see Section 5.3.5.6)
- Suspected transmission of an infectious agent by the study drug, as defined below:

Any organism, virus, or infectious particle (e.g., prion protein transmitting transmissible spongiform encephalopathy), pathogenic or non-pathogenic, is considered an infectious agent. A transmission of an infectious agent may be suspected from clinical symptoms or laboratory findings that indicate an infection in a patient exposed to a medicinal product. This term applies only when a contamination of the study drug is suspected.
- Grade ≥ 3 symptomatic hyperglycemia
- Grade ≥ 2 colitis or enterocolitis
- Grade ≥ 2 diarrhea
- Grade ≥ 3 rash
- Grade ≥ 2 pneumonitis

- Grade ≥ 3 stomatitis

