5.3.5.6 Abnormal Liver Function Tests

The finding of an elevated ALT or AST ($>3 \times$ baseline value) in combination with either an elevated total bilirubin ($>2 \times$ ULN) or clinical jaundice in the absence of cholestasis or other causes of hyperbilirubinemia is considered to be an indicator of severe liver injury. Therefore, investigators must report as an adverse event the occurrence of either of the following:

- Treatment-emergent ALT or AST $>3 \times$ baseline value in combination with total bilirubin $>2 \times$ ULN (of which $\geq 35\%$ is direct bilirubin)
- Treatment-emergent ALT or AST $>3 \times$ baseline value in combination with clinical jaundice

The most appropriate diagnosis or (if a diagnosis cannot be established) the abnormal laboratory values should be recorded on the Adverse Event eCRF (see Section 5.3.5.4) and reported to the Sponsor immediately (i.e., no more than 24 hours after learning of the event), either as a serious adverse event or a non-serious adverse event of special interest (see Section 5.4.2).

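### No taselisib/placebo hold or rechallenge limit is tied to meeting the protocol's own severe-liver-injury criteria, and the liver-function condition on continued dosing has no on-treatment threshold

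*Combined protocol and SAP*

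**What the plan says.** - **Definition and report.** Protocol Section 5.3.5.6 says that the combination of raised transaminases and raised bilirubin or jaundice "in the absence of cholestasis or other causes of hyperbilirubinemia is considered to be an indicator of severe liver injury". The reportable forms are ALT or AST above 3 × baseline with total bilirubin above 2 × ULN (at least 35% of it direct), or with clinical jaundice. The event is to be recorded and "reported to the Sponsor immediately (i.e., no more than 24 hours after learning of the event), either as a serious adverse event" or as a non-serious adverse event of special interest (AESI).
- **AESI list.** Section 5.2.3 includes "Cases of potential drug-induced liver injury that include an elevated ALT or AST in combination with either an elevated bilirubin or clinical jaundice". The duty stated there is again to report.
- **Liver management.** Section 5.1.1.1.5 requires liver function, judged on bilirubin and transaminases, to be adequate both at the start and for dosing to go on. It asks for a standard local work-up of new abnormalities and names liver metastases, concomitant drugs and biliary obstruction as frequent causes. On dosing it says: "Dose delay and modification for patients who experience abnormal liver function test results can also follow the guidelines in" a generic grid (Table 8). That pointer applies only "if deemed clinically appropriate by the investigator".
- **Table 8 (Section 5.1.1.1.9).** For a first Grade 3 event, hold until Grade 1 or lower, then: "Resume taselisib/placebo at the same dose or one dose level lower per investigator evaluation". The next row, "3, recurrent or 4, non-life threatening", holds and then resumes one level lower. Only a life-threatening Grade 4 event is a permanent stop.

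**The concern.** An event that the protocol itself classes as pointing to severe liver injury sets a reporting clock but no dosing rule. Whether the patient is held while the cause is sought, and whether she is re-exposed if none is found, depends on the grade assigned or on judgment by the site or the Sponsor. The avoidable harm is re-exposure after unexplained severe liver injury. Independent Data Monitoring Committee oversight ended with the primary PFS analysis (Sections 3.1 and 6.9.1), so for patients still on treatment that judgment now rests with the site and the Sponsor.

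**Working it through.** This is a check of rules against each other; there is no planned figure to reproduce.

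1. **What the trigger does.** Sections 5.3.5.6 and 5.2.3 lead to recording and a 24-hour report. Neither mentions dosing.

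2. **The condition on continued dosing.** Section 5.1.1.1.5 is mandatory in tone, so the next step is to look for the threshold. Numbers appear only in Section 4.1.1, for results within 28 days before Cycle 1 Day 1: total bilirubin at most 1.5 × ULN (at most 3 mg/dL with documented Gilbert's syndrome); AST and ALT at most 1.5 × ULN, or at most 5.0 × ULN with liver metastases. Bilirubin above 2 × ULN would exceed the general screening limit, but no text carries that limit into the treatment period or states an action when it is passed.

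3. **Table 8.** It is reached in two ways: optionally from Section 5.1.1.1.5, and through Section 5.1.1.1.9 for other clinically significant events, without the discretion clause. Its rows are Grade 3 first event, Grade 3 recurrent or Grade 4 non-life-threatening, and Grade 4 life-threatening. Section 5.3.5.6 uses multiples of baseline and ULN with no grade. The CTCAE cut-offs are not in the documents, so the two cannot be mapped onto each other. Where a Grade 3 row does apply, same-dose resumption is expressly allowed.

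4. **General routes to a stop.** Section 4.6.2 requires discontinuation for unacceptable toxicity, or for a condition that the investigator or Sponsor judges unsafe. Section 5.1.1.1 allows more conservative holds. Sections 5.5.2 and 5.7 have the Sponsor evaluate serious events and AESIs. All turn on judgment; none refers to Section 5.3.5.6.

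5. **Comparison with the other AESIs.** Section 5.2.3 lists 8 items. Leaving out suspected contamination of study drug gives 8 − 1 = 7 drug toxicities. Hold stated at the reporting grade:
   - Unconditional, 5: Grade 2 diarrhea and Grade 2 colitis (Table 3), Grade 3 stomatitis (Table 4), Grade 3 rash (Table 6), Grade 3 symptomatic hyperglycemia (Table 7).
   - While corticosteroids are given, 1: Grade 2 pneumonitis (Table 5).
   - None, 1: liver injury.

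   5 + 1 + 1 = 7.

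6. **Comparison of resumption rules.** After a first Grade 3 event, Tables 3 to 7 resume one level lower (Table 3 lets confirmed infectious diarrhea resume at the same dose with Medical Monitor approval). Table 8 allows the same dose. At Grade 4, Tables 3 to 6 stop permanently, while Table 7 allows resumption after a first event and Table 8 allows it if the event is not life-threatening.

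7. **Scale.** The documents count no case meeting Section 5.3.5.6. The nearest figures, in Section 1.3.2, are drug-related Grade 3 to 4 enzyme events: raised transaminases in 1% of 83 on taselisib plus fulvestrant, and raised ALT in 1% of 108 on taselisib alone. A reported 1% means 0.5% to 1.5%: 0.4 to 1.2 patients of 83 and 0.5 to 1.6 of 108, so one patient each. Together (1 + 1)/(83 + 108) = 2/191 = 1.05%, exact (Clopper–Pearson) 95% CI 0.13% to 3.73%. No bilirubin rise is stated and capsule doses were mixed, so this shows scale for enzyme events only.

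**The case against.** The strongest reply comes from the liver section itself. It makes adequate liver function a requirement for continued dosing, and a patient with bilirubin above 2 × ULN hardly meets it. A reader might therefore be tempted to overstate the gap in two ways: that optional Table 8 is the only liver dosing text, or that the plan affirmatively allows dosing through the work-up. The documents support neither. The continued-dosing sentence is mandatory, and Section 5.1.1.1.9 sends clinically significant events to Table 8 without the discretion clause, so a Grade 3 or 4 liver event would be held by grade. What remains is narrower: the requirement has no on-treatment number, hold or resumption rule, and nothing links it to Section 5.3.5.6. Nor can one say that qualifying events fall below Grade 3 and escape Table 8, because the grading cut-offs are not given.

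A second objection concerns rechallenge. Resumption after a first Grade 3 event is the norm in Tables 3 to 7, so permanent discontinuation after one unexplained event would be stricter than most of the protocol's first-event rules. That stands. A reader might infer from the AESI comparison that the protocol already bars first-event rechallenge elsewhere; below Grade 4 it does not. The stricter limit has to rest on what the event is: the protocol's own sign of severe liver injury, with no other cause found.

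Third, the expected effect is small. Liver injury is not among the selected toxicities of interest in Section 5.1.1, and the new adverse drug reactions listed in Section 1.3.2 after unblinding (infection, alopecia, fever, dyspepsia, weight loss) are not hepatic. This also stands. It limits the size of the point without closing the gap.

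**Conclusion.** The gap is real but narrow. Section 5.1.1.1.5 sets a condition on continued dosing without defining it, and no section attaches a hold or a limit on rechallenge to an event meeting Section 5.3.5.6. Dose action falls to general judgment or to a grade-keyed table that is more permissive on resumption than Tables 3 to 7 at Grade 3, and more permissive than Tables 3 to 6 at Grade 4.

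Few patients are concerned, and only those still on taselisib/placebo. The number cannot be estimated: a reader might take the 1.05% enzyme figure as a Hy's law rate, but nothing in the documents makes it one. The case rests on the severity of the event and on re-exposure being avoidable, and assumes that sites would otherwise vary in how they act. It is a low-cost safety improvement and does not call any efficacy result into question.

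**What to change.** Add one paragraph to Section 5.1.1.1.5:

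- ALT or AST above 3 × baseline with total bilirubin above 2 × ULN, or with clinical jaundice, means that liver function is not adequate for continued dosing. Hold taselisib/placebo at once.
- Complete the work-up, including direct bilirubin.
- Do not resume under Table 8, and discontinue permanently, unless another cause is documented (for example biliary obstruction, a concomitant medication or liver metastases).

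The hold is set off by the laboratory values or jaundice because absence of another cause is known only after the work-up; the rechallenge limit then applies only to unexplained cases. If direct bilirubin is below 35% of total and there is no jaundice, Section 5.3.5.6 is not met and ordinary management resumes. Confirmed progression stops study drug under Section 4.6.2 in any case. Screening limits and Table 8 otherwise stay as they are.

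Cost: the paragraph, a site memo, and one event-driven test. Section 5.3.5.6 already needs direct bilirubin for its laboratory criterion, but the routine panels in Section 4.5.6 and Appendix 1 list only total bilirubin. The clinical downside is a short interruption for a few patients whose event proves to have another cause. No endpoint definition, blinding arrangement or planned analysis changes.

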5.1.1.1.6 Management of Asymptomatic Lipase and/or Amylase Elevations

Some patients who have been treated with taselisib have experienced asymptomatic lipase and/or amylase elevations in blood tests without any clinical or radiographic

symptoms of pancreatitis or another clear etiology for the abnormal laboratory test values. Elevated lipase may sometimes be associated with corticosteroid treatment. Upon discussion with the Medical Monitor and after a benefit-risk assessment, investigators may consider continuing tasisib therapy in such patients at the same dose or one dose level lower. Investigators should have a low threshold for interrupting tasisib/placebo for any clinical gastrointestinal toxicities of concern.

5.1.1.1.7 Potential Inflammatory or Immunosuppressant Effects

On the basis of tasisib data from nonclinical toxicity studies showing changes in WBC and absolute lymphocyte and/or neutrophil counts, patients will be required to have adequate hematologic function to participate in the study, and any bone marrow toxicities from prior therapies must be resolved before initiation of tasisib. Patients will be monitored throughout the study treatment for changes in blood counts and signs of infection. Dose delay and modification for patients who experience changes in blood counts or show signs of infections can also follow the guidelines in [Table 8](#) if deemed clinically appropriate by the investigator.

5.1.1.1.8 Infection

At the time of the primary PFS analysis of Study GO29058, 41.8% of patients in the tasisib arm had developed infections compared with 23.9% of patients in the control (placebo) arm. Serious infections occurred in 7.5% of patients in the tasisib arm compared with 0.9% of patients in the control (placebo) arm. A total of 0.5% of patients died on account of infection in the tasisib arm compared with no patients in the control (placebo) arm.

Urinary tract infections were the most commonly reported infection; however, respiratory tract, gastrointestinal tract, and skin infections were also common in the tasisib arm.

Investigators and patients should be aware of the increased risk of infection with tasisib. If a diagnosis of infection is made, appropriate treatment should be initiated promptly and consideration given to holding or discontinuing tasisib/placebo as per the guidelines in [Table 8](#).

5.1.1.1.9 Management of Other Clinically Significant Adverse Events

See [Table 8](#) for the dose modifications for other clinically significant adverse events.

Table 8 Taselisib/Placebo Dose Delay and Modification Guidelines for Other Clinically Significant Adverse Events

Grade	Taselisib/Placebo
3, first event	Hold taselisib/placebo until Grade \leq 1. Resume taselisib/placebo at the same dose or one dose level lower per investigator evaluation.
3, recurrent or 4, non-life threatening	Hold taselisib/placebo until Grade \leq 1. Resume taselisib/placebo dosing at one dose level lower.
4, life-threatening	Permanently discontinue taselisib/placebo. Single-agent fulvestrant may be continued per investigator evaluation.

